### **Part 2**

Participants will not be replaced unless they fail to begin study treatment.

## **12.4 Statistical Analysis**

### **12.4.1 Primary Endpoint Analysis**

#### **Part 1**

The primary objective is to assess the safety and tolerability of itacitinib and ECP in subjects with chronic GVHD and to determine the RP2D. Adverse events (AEs), serious adverse events (SAEs), and dose-limiting toxicities (DLTs) are primary endpoints.

All subjects who receive any study treatment will be included in the final summaries and listings of safety data. Detailed information collected for each AE will include a description of the event, duration, severity, relatedness to study drugs, action taken, and clinical outcome. The severity of the AEs will be graded according to the CTCAE v5.0. The statistical analysis of the safety data will be descriptive and tabular in nature.

## Part 2

Simon's optimal two-stage design will be used in Part 2. The primary outcome is the overall response rate (CR + PR) at 24 weeks. Withdrawal or progression prior to 24 weeks or missing 24-week assessment will be considered non-response. After the first 16 patients treated at the RP2D complete 24 weeks of therapy or meet treatment discontinuation criteria, enrollment will be put on hold and an interim analysis will be conducted. This study treatment will be considered promising if the overall response rate at 24 weeks is  $\geq 60\%$  and unacceptable if the overall response rate at 24 weeks is  $\leq 40\%$ . 50% is the reported best overall response rate of current first-line therapy with high-dose steroids. The null hypothesis that the true response rate is  $\leq 40\%$  will be tested against a one-sided alternative.

In the first stage of the dose-expansion study, 16 patients will be accrued and followed through the first 24 weeks of treatment. Of those 16 patients, 6 patients will be carried over from Part 1 at the RP2D. In recognition of a potential accrual pause of at least 24 weeks if all 16 patients are required to complete six months of combination therapy, we will permit enrollment of an additional 3 patients (20%) after the first 10 eligible patients in the first stage of the dose-expansion study are enrolled if no more than 5 of 16 patients have experienced treatment failure (i.e. addition of secondary systemic therapy or disease relapse or death) by the end of week 12 of treatment. If there are 7 or fewer responses in the first 16 patients enrolled, the study will be stopped. Otherwise, 30 additional patients will be accrued for a total of 46. The null hypothesis will be rejected if 24 or more responses are observed in 46 patients. This design yields a type I error rate of 0.0486 and a power of 80% when the true response rate is  $\geq 60\%$ .

Exact binomial confidence intervals for response will be reported at the end of the trial.

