## 1 OBJECTIVES

### 1.1 Primary Objective

**1.1.1 Part 1:** To assess an appropriate dose of itacitinib in combination with Extracorporeal Photopheresis (ECP) in patients with moderate or severe chronic GVHD.

Primary Endpoint: The rate of dose-limiting toxicities during the defined DLT evaluation period.

**1.1.2 Part 2:** To assess the clinical efficacy of itacitinib in combination with ECP in subjects with moderate or severe chronic GVHD treated at the Recommended Phase 2 Dose (RP2D).

Primary Endpoint: Overall response rate (ORR) at 24 weeks (at Cycle 7 Day 1 visit) as determined by the NIH Consensus Development Project Criteria (ORR is defined as CR + PR) without secondary systemic immunosuppressive therapy and no recurrent malignancy or death.

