## 4 STUDY DESIGN

### 4.1 Description

This is an open-label, Phase II trial designed to assess the recommended phase 2 dose (RP2D) of itacitinib in combination ECP and efficacy of the combination after 24 weeks of therapy. The trial will consist of two parts: Part One will assess the RP2D. For dose-finding purposes, the DLT evaluation period will be defined as the time from the first dose of itacitinib lead-in (7-day lead-in) to the last day of cycle one combination therapy (cycle one day 28). Part Two will further describe and characterize the safety and efficacy of the regimen. The RP2D will be determined by a 3+3 dose de-escalation design. Should dose level one be deemed intolerable, enrollment will proceed at dose level -1. The RP2D will be affirmed according to the rules of the 3+3 dose de-escalation scheme (Section 4.2). Once an RP2D has been confirmed, Part 2 will open as an expansion cohort. Safety will be monitored during the trial as described in Section 11.3.

All eligible patients will begin study therapy with approximately a week lead-in of itacitinib monotherapy. After completing the itacitinib lead-in, combination treatment will begin in 28-day cycles. After eight weeks of combination therapy, patients will begin an ECP taper and continue on itacitinib for a total of 6 cycles. Patients achieving PR or better may

continue on itacitinib for up to 1 year. Patients will remain on study therapy as long as treatment discontinuation criteria are not met.

Prednisone dose (or prednisone equivalent) at  $\leq 0.25$  mg/kg/d for treatment of GVHD progressing or not sufficiently responding to study treatment will be allowed, at the discretion of the treating investigator and with approval of the PI, while the participant is on study treatment. Addition of prednisone dose (or prednisone equivalent) at  $\leq 0.25$  mg/kg/d will not be considered as failure of the primary endpoint. Prednisone doses (or prednisone equivalent) of  $> 0.25$  mg/kg/d but  $\leq 0.5$  mg/kg/d for more than 8 weeks or  $> 0.5$  mg/kg/d once will count as a failure of the primary endpoint, but the participant will be allowed to remain on the treatment period of the study. If the participant requires any systemic immunosuppression besides prednisone (i.e., ibrutinib, ruxolitinib, etc.), the participant will be withdrawn from study treatment but remain on study for follow-up.

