## 12 STATISTICAL CONSIDERATIONS

### 12.1 Sample Size Determination

#### Part 1

Part 1 has a maximum of 18 patients. Part 1 has a 3+3 dose de-escalation design with 3 doses and a maximum of 6 patients per dose.

#### Part 2

The sample size for Part 2 is 16-46 patients with 6 patients carried over from Part 1 at the RP2D. Simon’s optimal two-stage design will be used in Part 2. The primary outcome is the overall response rate (CR + PR) at 24 weeks. Withdrawal or progression prior to 24 weeks or missing 24-week assessment will be considered non-response. After the first 16 patients treated at the RP2D complete 24 weeks of therapy or meet treatment discontinuation criteria, enrollment will be put on hold and an interim analysis will be conducted. This study treatment will be considered promising if the overall response rate at 24 weeks is  $\geq 60\%$  and unacceptable if the overall response rate at 24 weeks is  $\leq 40\%$ . 50% is the reported best overall response rate of current first-line therapy with high-dose steroids. The null hypothesis that the true response rate is  $\leq 40\%$  will be tested against a one-sided alternative.

In the first stage of the dose-expansion study, 16 patients will be accrued and followed through the first 24 weeks of treatment. Of those 16 patients, 6 patients will be carried over from Part 1 at the RP2D. In recognition of a potential accrual pause of at least 24 weeks if all 16 patients are required to complete six months of combination therapy, we will permit enrollment of an additional 3 patients (20%) after the first 10 eligible patients in the first stage of the dose-expansion study are enrolled if no more than 5 of 16 patients have experienced treatment failure (i.e. addition of secondary systemic therapy or disease relapse or death) by the end of week 12 of treatment. If there are 7 or fewer responses in the first 16 patients enrolled, the study will be stopped. Otherwise, 30 additional patients

will be accrued for a total of 46. The null hypothesis will be rejected if 24 or more responses are observed in 46 patients. This design yields a type I error rate of 0.0486 and a power of 80% when the true response rate is  $\geq 60\%$ .

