addition of new systemic treatment for chronic GVHD, and use of prednisone dose (or its equivalent) of  $\leq 0.5$  mg/kg/d at 24 weeks. Kaplan-Meier methods will be used for these binary endpoints if there are censored events. Kaplan –Meier methods and associated confidence intervals will be used for survival endpoints (FFS and OS). NRM and RR will be treated as competing risks and analyzed by computing nonparametric subdistribution functions. The minimum, maximum, mean, and median value along with interquartile range will be reported for continuous and ordered categorical endpoints (NIH global score of chronic GVHD, provider, and patient-reported GVHD severity). Change in continuous or ordered categorical endpoints (NIH global score of chronic GVHD, provider, and patient-reported GVHD severity) will be analyzed using paired Wilcoxon tests. The minimum, maximum, mean, and median cumulative prednisone dose at 24 weeks will be reported, along with the interquartile range.

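### The sections that carry the Simon test count CR + PR at 24 weeks without the endpoint conditions of 1.1.2 and 4.1, so one foreseeable type of patient is a responder in one place and a failure in another

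*Combined protocol and SAP*

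**What the plan says.** Section 1.1.2 makes the Part 2 primary endpoint a composite at Cycle 7 Day 1: "ORR is defined as CR + PR) without secondary systemic immunosuppressive therapy and no recurrent malignancy or death". Section 4.1 then says how prednisone bears on that endpoint. Doses up to 0.25 mg/kg/d are not a failure. A single dose above 0.5 mg/kg/d, or more than 8 weeks at doses above 0.25 and up to 0.5 mg/kg/d, is treated differently. Of such use the section says that it "will count as a failure of the primary endpoint, but the participant will be allowed to remain on the treatment period of the study".

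The sections that carry the test describe the outcome differently. The Study Summary, 12.1 and 12.4.1 share one paragraph, which reads: "The primary outcome is the overall response rate (CR + PR) at 24 weeks. Withdrawal or progression prior to 24 weeks or missing 24-week assessment". Each of these three events is then classed as non-response, and no other event is named. Section 4.4 counts CR or PR for the interim decision. None of these sections refers to 1.1.2 or 4.1 for the response count. The decision rules are: "If there are 7 or fewer responses in the first 16 patients enrolled, the study will be stopped"; otherwise accrual continues to 46, and the null is rejected at 24 or more responses. On performance: "This design yields a type I error rate of 0.0486 and a power of 80% when the true response rate is" 60% or more.

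Section 12.4.2 writes out the full composite for the secondary 1-year response rate. It also lists, as possible separate binary endpoints, absence of recurrent malignancy, no "addition of new systemic treatment for chronic GVHD, and use of prednisone dose (or its equivalent) of" at most 0.5 mg/kg/d at 24 weeks.

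**The concern.** One primary endpoint has two descriptions, and the shorter one sits next to the decision rules. The omission is hard to read as plain shorthand. The same chapter spells out the conditions for the 1-year rate. The paragraph holding the decision rules also names secondary therapy, relapse and death as treatment failure, but only for the week-12 rule on enrolling 3 extra patients.

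The trial is single-arm and open-label, and its reference is the historical response to high-dose steroids. Responses reached with the help of added steroids are the ones whose classification must be fixed in advance. The protocol expects them: 4.1, 6.1.3 and 6.7.1 all let a patient stay on study treatment after prednisone use that counts as failure, and 12.4.2 plans a 24-week response rate in a stratum above 0.25 mg/kg/d. If such patients enter the counts, the stated type I error belongs to a looser endpoint than the one in 1.1.2.

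**Working it through.** **Step 1. Reproduce the design.** Inputs from 12.1 and 12.4.1: null rate 0.40, alternative 0.60, 16 patients in stage 1 with a stop at 7 or fewer responses, 46 in total (30 in stage 2), rejection at 24 or more.

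P(reject | p) = Σ from x = 8 to 16 of C(16, x) pˣ (1 − p)¹⁶⁻ˣ × P(Bin(30, p) ≥ 24 − x)

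- p = 0.40: 0.0486, which agrees with the plan.
- p = 0.60: 0.8006, which agrees with the stated 80%.
- Probability of stopping at stage 1: 0.716 at p = 0.40 and 0.142 at p = 0.60.

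**Step 2. Classify each type of patient under both texts.**

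| Patient | 12.4.1 as written | 1.1.2 with 4.1 |
|---|---|---|
| Dies before week 24 | Non-response (no assessment) | Failure |
| Progresses before week 24 and exceeds the 4.1 steroid limits | Non-response (progression) | Failure |
| Receives another systemic immunosuppressant, or relapses | Non-response only if withdrawal includes stopping study treatment | Failure |
| No progression, prednisone within the 4.1 allowance, CR or PR at Cycle 7 Day 1 | Responder | Responder, by the express words of 4.1 |
| No progression, exceeds the 4.1 steroid limits, stays on treatment, CR or PR at Cycle 7 Day 1 | **Responder** | **Failure** |

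The last row is a direct conflict. The third row depends on a word the plan does not define. Under 6.7.1 a patient given another immunosuppressant leaves study treatment but remains in follow-up, so a later response assessment may exist.

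**Step 3. Effect on a decision.** Suppose 24 of 46 patients are in CR or PR and one is a last-row patient. Section 12.4.1 counts 24 and rejects. Sections 1.1.2 and 4.1 count 24 − 1 = 23 and do not. At the interim the same happens with 8 against 7.

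**Step 4. Size, under assumption.** Let m be the share of all patients who are in CR or PR at week 24 and are counted, but fail the 1.1.2 and 4.1 conditions. The documents give no value for m. Hold the true qualifying rate at the null of 0.40; the counted rate is then 0.40 + m, which goes into the Step 1 formula.

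| m | Counted rate | Expected patients in 46 (46 × m) | P(reject) | P(stop at stage 1) |
|---|---|---|---|---|
| 0 | 0.40 | 0 | 0.049 | 0.716 |
| 2% | 0.42 | 0.9 | 0.082 | 0.657 |
| 5% | 0.45 | 2.3 | 0.160 | 0.563 |
| 10% | 0.50 | 4.6 | 0.360 | 0.402 |

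**The case against.** The strongest reply is that the protocol should be read as a whole. Section 1.1.2 is the labelled primary endpoint, and 4.1 addresses the disputed patient directly. Section 12 never says that it replaces either, and its non-response sentence does not say that its list is complete. A reader might infer from section 12 that every patient rescued with steroids who stays on treatment counts as a responder in the Simon test. The documents do not support that. Section 4.1 says that exposure above its limits is a failure. Rescue at or below 0.25 mg/kg/d can coexist with response because 4.1 allows it, not because section 12 is silent. Steroid given for progression falls under the progression rule of 12.4.1 itself. Death is covered too, and relapse and other immunosuppression probably are. Section 6.6.4 also lists prednisone above 0.5 mg/kg/d for GVHD as prohibited, which narrows the group further.

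These points stand, and they confine the problem to the last row of the table plus the undefined word. They do not remove it. An analyst who applies 12.4.1 as written obtains the opposite result to 4.1 for that patient, and no text says which section governs the two counts. Nor does 4.1 supply one settled rule: 1.1.2 excludes secondary systemic immunosuppression without qualification, and 6.1.3 requires a dose strictly below 0.25 mg/kg/d after 8 weeks, whereas 4.1 accepts 0.25 itself.

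It is also fair to say that listing components separately in 12.4.2 does not take them out of a composite, and that the stratified response rate would make steroid-associated responses visible. Neither settles the primary count.

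**Conclusion.** The concern holds as a conflict of definitions, not as a calculation error. The boundaries, the 0.0486 and the 80% are right for whatever endpoint is counted. What is unsettled is whether a patient without progression who meets the 4.1 steroid failure rule, stays on treatment and is in CR or PR at Cycle 7 Day 1 is counted. Relapse and other immunosuppression add to this only if withdrawal does not include discontinuation of study treatment.

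The size rests wholly on an assumed share of such patients. With a true qualifying rate of 40%, shares of 2%, 5% and 10% give false-positive probabilities of about 0.08, 0.16 and 0.36, against 0.0486 when nobody is miscounted. The affected group is narrow, so the larger shares should not be taken as likely. Because a single patient can decide 23 against 24, the definition should be settled before the interim count.

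**What to change.** - In the Study Summary, 4.4, 12.1 and 12.4.1, use one responder definition for both the 7/16 and the 24/46 counts: CR or PR at Cycle 7 Day 1 that meets the 1.1.2 conditions, with failure through secondary therapy determined by reference to 4.1. Withdrawal, progression or a missing assessment remains non-response.
- State that withdrawal includes discontinuation of study treatment.
- The sponsor should reconcile the steroid-failure wording in 1.1.2, 4.1, 6.1.3 and 6.7.1, so that 4.1 can serve as the single reference. Two further points belong there. Section 4.1 does not expressly classify doses above 0.25 and up to 0.5 mg/kg/d given for 8 weeks or less. It also permits low-dose prednisone for progressing GVHD without endpoint failure, while 12.4.1 makes progression non-response. This review does not choose the threshold.

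The cost is wording in the four sections that carry the counts, plus the reconciliation. Boundaries and sample size do not change. No new data are needed, because the Schedule of Events already records systemic corticosteroid dose at the treatment visits. The downside is that the reported response rate may be slightly lower.

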### 12.4.2 Secondary Endpoint Analysis

#### Safety

Toxicity in this trial will be defined as Dose Limiting Toxicities identified in Section 4.3 attributable to the study therapy. If the observed rate of DLTs exceeds 30% during Part 2 portion, the trial will be stopped.

A safety analysis will be conducted on the safety population, which includes enrolled subjects who receive at least one dose of study drug (itacitinib) and one ECP treatment. The baseline value is defined as the last value collected on or prior to the first dose date of the study drug. The safety variables to be analyzed include exposure of the study drug, AEs, clinical laboratory test results, Karnofsky/Lansky performance status, physical examination, and vital sign measurements. In general, safety data will be tabulated or listed. Descriptive statistics will be used to tabulate toxicities.

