
*Short Title: FLIGHT*

*Version Date: 28JAN2022*

	subjects who receive at least 1 dose of itacitinib and one ECP treatment.
--	---

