 Monitoring for infection will be performed at screening and for the duration of study therapy per institutional practice. Testing for cytomegalovirus and Epstein-Barr virus will be performed at screening. Prior test results obtained as part of standard of care before allo-HCT may be used for purposes of eligibility and tests do not need to be repeated. Routine infection monitoring should occur during the study as per institutional practice and include at a minimum PCR

testing on plasma for CMV and EBV and monitoring for fungal infections (i.e. Aspergillus). Additional monitoring should be performed during treatment if there is clinical suspicion of an infection.

 Screening assessment may be used if completed within 7 days prior to C1D1.

 Graft failure/chimerism should be performed on whole blood and should include: Chimerism, Post-Transplant and Chimerism, Post-Cell Sort, T cells.

 Participants will be closely monitored for any evidence of underlying disease relapse or recurrence during study therapy. These evaluations will be conducted in accordance with local institutional practices.

 To be completed prior to the physical exam at C1D1, C2D1, C3D1, C6D1, C8D1, C10D1, and EOT or PD visit.

 ECP will be given at a frequency of twice weekly for 8 weeks followed by a standard taper schedule as per study protocol. Refer to Table 4 for taper schedule.

 All patients will undergo 5 to 10 days of itacitinib monotherapy. The first ECP treatment will be considered C1D1. On days that the patient is being seen in clinic, itacitinib dosing does not need to be held prior to routine blood draws or for correlative studies.

 Patients may be on immune suppression at the time of study enrollment. On days that the patient is being seen in clinic, immunosuppressives should be held until after the blood draws if trying to achieve a therapeutic level. See Section 6.1.3.

 Correlative studies are only required during dose expansion. On days of drug administration, correlative blood samples should be drawn without regard to itacitinib dosing or ECP therapy. Patients should take itacitinib at their usual time. Blood will be drawn at screening, C1D1, the time of response, C7D1, and at EOT or progression, whichever occurs first.

 Only to be drawn from the first nine patients enrolled in Part 2, Dose Expansion.

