### **12.2.2 Evaluable for toxicity**

All patients who have received at least one dose of itacitinib will be evaluable for toxicity assessment.

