#### **16.4 Adverse Events**

An adverse event is the appearance or worsening of any undesirable sign, symptom, or medical condition occurring after starting the study drug even if the event is not considered to be related to study drug. For the purposes of this study, the terms toxicity and adverse event are used interchangeably. Medical conditions/diseases present before starting study drug are only considered adverse events if they worsen after starting study drug. Abnormal laboratory values or test results constitute adverse events only if they induce clinical signs or symptoms, are considered clinically significant or require therapy.

Collection of adverse events will begin with the initiation of study therapy and end 30 days after the last dose of study drug (or until new cancer treatment is initiated).

Information about all adverse events, whether volunteered by the subject, discovered by investigator questioning, or detected through physical examination, laboratory test or other means, will be collected, recorded and followed as appropriate.

The adverse event should be evaluated to determine:

1. The severity grade based on CTCAE v5.0 (grade 1-5)
2. Its relationship to itacitinib, ECP, GVHD, and transplant associated therapies (i.e. transplant, conditioning regimen, or immunosuppressants) (definite, probable, possible, unlikely, not related)
3. Its duration (start and end dates or if continuing at the final exam)
4. Action taken (no action taken; study drug dosage adjusted/temporarily interrupted; study drug permanently discontinued due to this adverse event; concomitant medication taken; non-drug therapy given; hospitalization/prolonged hospitalization)
5. Whether it constitutes an SAE

All adverse events will be treated appropriately. Such treatment may include changes in study drug treatment as listed in the dose modification section of this protocol (see Section 8 for guidance). Once an adverse event is detected, it should be followed until its resolution, and assessment should be made at each visit (or more frequently, if necessary) of any

changes in severity, the suspected relationship to the study drug, the interventions required to treat it, and the outcome.

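### The safety population in Section 12.4.2 and the Study Summary requires an ECP treatment, so a patient who stops for toxicity in the itacitinib-only lead-in is left out of the safety tables, contrary to Section 12.2.2 and, for Part 1, Section 12.4.1

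*Combined protocol and SAP*

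**What the plan says.** Three rules say who belongs in the safety analysis.

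- **Section 12.4.2 (Safety):** the safety population is the set "which includes enrolled subjects who receive at least one dose of study drug (itacitinib) and one ECP treatment". The Study Summary, under Statistical Methodology, has the same rule: "subjects who receive at least 1 dose of itacitinib and one ECP treatment".
- **Section 12.2.2:** "All patients who have received at least one dose of itacitinib will be evaluable for toxicity assessment". It has no ECP condition and is not limited to one Part.
- **Section 12.4.1, under the Part 1 heading:** "All subjects who receive any study treatment will be included in the final summaries and listings of safety data".

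The treatment sequence is the same for everyone. Section 4.1 states: "All eligible patients will begin study therapy with approximately a week lead-in of itacitinib monotherapy". Footnote 26 of the Schedule of Events (Table 7) adds: "All patients will undergo 5 to 10 days of itacitinib monotherapy. The first ECP treatment will be considered C1D1".

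The lead-in is inside the safety observation period. Section 16.4 states: "Collection of adverse events will begin with the initiation of study therapy and end 30 days after the last dose of study drug". Sections 4.1 and 4.3 open the DLT window at the first lead-in dose. Section 7.1 says that a patient whose toxicity meets DLT criteria in that window should come off treatment, unless continuation is approved for clinical benefit.

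On replacement in Part 2, Section 12.3 states: "Participants will not be replaced unless they fail to begin study treatment".

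**The concern.** A patient who has taken itacitinib but has not reached the first ECP session is in the toxicity set of Section 12.2.2 and outside the safety population of Section 12.4.2. Both rules cannot govern the same tables.

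The exclusion can also depend on the outcome. Serious toxicity in the lead-in is a natural reason for never reaching ECP, and Section 7.1 makes stopping the default after a DLT. The event then removes the patient from the analysis meant to report it. Safety is the first secondary objective (Section 1.2.1), and the events at risk of omission are early toxicities on the investigational drug.

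Section 12.4.2 is also internally awkward. It sets baseline by the first dose of study drug, which it identifies as itacitinib, and then drops patients who received only that drug.

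**Working it through.** **1. The definitions, applied to one patient.** Take a patient who has a DLT on lead-in day 4, is taken off treatment and never receives ECP.

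- Section 16.4: the event is collected.
- Section 4.3: it falls in the DLT window.
- Section 12.2.1 (Part 1): the patient is evaluable for dose tolerability, because having had a DLT suffices.
- Section 12.2.2 (either Part): included.
- Section 12.4.1 (Part 1): included.
- Section 12.4.2 and the Study Summary: excluded.
- Section 12.3 (Part 2): not replaced, so the patient remains an enrolled, treated patient.

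A patient with a lead-in event who goes on to receive ECP stays in every set. The conflict concerns only those who never reach ECP.

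**2. The plan's own figures.** None depends on this definition, and they reproduce.

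- Two-stage design: P(reject) = Σ over x = 8 to 16 of P(X₁ = x) × P(X₂ ≥ 24 − x), with X₁ ~ Bin(16, p) and X₂ ~ Bin(30, p). This gives 0.0486 at p = 0.40 and 0.8006 at p = 0.60, matching the stated 0.0486 and 80%.
- Table 11: an exact binomial recursion, with looks after each patient from 7 to 46 and stopping when the count exceeds the listed limit, reproduces all six rows (for example 0.098 with expected size 43.3 at a 15% rate, and 0.987 with 13.7 at 40%).

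**3. Direction of the effect.** Let N patients be treated and x have the event. Suppose k patients with the event and m without it leave before ECP. All treated patients give x/N; the Section 12.4.2 set gives (x − k)/(N − k − m). Cross-multiplying, the second is lower exactly when k/(k + m) > x/N, that is, when the event is more common among lead-in leavers than overall. If every leaver had the event (m = 0), the rate falls whenever x < N. If none had it (k = 0), the rate rises whenever x > 0.

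**4. Size, under assumed counts.** N = 46 comes from Section 12.1. The documents give no lead-in loss or toxicity rate, so k, m and x are assumptions.

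| Lead-in leavers | All treated | Section 12.4.2 set |
|---|---|---|
| 2 with the event | 10/46 = 21.7% | 8/44 = 18.2% |
| 1 with the event | 8/46 = 17.4% | 7/45 = 15.6% |
| 1 with, 1 without | 10/46 = 21.7% | 9/44 = 20.5% |
| 2 without the event | 8/46 = 17.4% | 8/44 = 18.2% |
| none | 10/46 = 21.7% | 10/46 = 21.7% |

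**5. Chance that the question arises.** If each patient independently has probability q of stopping in the lead-in, the chance of at least one among 46 is 1 − (1 − q)^46: 37% at q = 1%, 60% at 2% and 91% at 5%. These q values are also assumptions.

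**6. The 30% sentence.** Section 12.4.2 says the trial stops if the Part 2 DLT rate exceeds 30%, names no denominator, and then defines the safety population. If that population were the denominator, a single lead-in DLT could reverse the reading: 4/13 = 30.8% for all treated, against 3/12 = 25.0% after exclusion.

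**The case against.** The strongest reply is that little turns on this population. The Section 12.4.2 analysis is tabular, with no hypothesis test. Lead-in events are still collected, and SAEs reach the medical monitor and the DSMC whatever set the final tables use (Sections 16.3 and 16.5.1). All of that stands, and it limits the importance of the point.

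Four stronger readings are tempting, and the documents do not support them.

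- *Lead-in toxicity escapes the stopping rule.* The numeric boundary in Section 11.3.2 counts patients treated at the RP2D, with no ECP condition. It also counts grade 3 or higher non-hematologic events, whereas Section 12.4.2 defines toxicity as DLTs. A gap between monitoring counts and final tables could therefore arise whatever population is used.
- *Dose finding loses lead-in DLTs.* Section 12.2.1 keeps any patient with a DLT evaluable.
- *Reported rates are always too low.* Step 3 shows that this holds only when leavers have the event more often than patients overall. Departures for consent withdrawal or relapse push the other way.
- *Section 12.4.1 contradicts the Part 2 analysis.* Its sentence stands under Part 1. The direct Part 2 conflict is with Section 12.2.2. Section 12.4.2 is not itself limited to Part 2, so its conflict with 12.4.1 is real for Part 1 patients.

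The reply does not remove the contradiction, nor the fact that a toxicity stop in the lead-in excludes the patient because of the toxicity.

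**Conclusion.** The point holds as a contradiction between definitions, with a predictable effect on the descriptive safety tables. Followed as written, Section 12.4.2 omits patients who stop for toxicity before ECP and so understates the rate of those events. In the illustrations where every leaver had the event, the shift is about 2 to 3.5 percentage points (17.4% to 15.6%, and 21.7% to 18.2%). It is nil if everyone reaches C1D1 and slightly upward if the leavers did not have the event. These sizes rest wholly on assumed counts.

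No stated design figure changes, and neither Part 1 DLT evaluability nor the numeric Part 2 boundary is shown to be affected. The one decision rule left open is the 30% DLT sentence, whose denominator is unstated. A reader might infer that the safety monitoring itself is compromised; the documents do not show that. This should be corrected before analysis, since choosing between definitions once lead-in events are known would be data-driven. It does not threaten the trial's primary conclusions.

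**What to change.** - Remove the ECP condition from the safety population in Section 12.4.2 and the Study Summary.
- State one definition in identical words in the Study Summary and Sections 12.2.2, 12.4.1 and 12.4.2, for example: *every patient who takes at least one dose of itacitinib, whether or not ECP is ever given*. Because itacitinib always comes first, this should be the same set as all patients given any study treatment.
- Use it for the AE, SAE and toxicity tables, and name it as the denominator of the 30% DLT sentence.
- Optionally, add a descriptive table of patients who received both components, to keep a view of the combination.

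The cost is a wording change in four places, with no effect on sample size, error rates or data collection. Reported rates may change slightly, usually in the less favourable direction.
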